4.3. PRIMARY ANALYSIS

The primary analysis for a candidate agent will take place after:

- Approximately 350 patients have been randomized to the candidate agent plus SoC active arm of the sub-protocol of interest and approximately 350 patients have been randomized to the shared placebo plus SoC control arm of the sub-protocol of interest (refer to Section 4.5), and last patient randomized into one of these two arms is from the sub-protocol of interest, because if the last randomized patient is from a sub-protocol other than the one of interest, the patient’s treatment arm will automatically be unblinded since those patients can only be included in the shared placebo plus SoC control arm of the sub-protocol of interest;
- The last patient randomized to that candidate agent plus SoC treatment arm or its concurrent shared placebo plus SoC control arm have had the opportunity to complete the Day 29 study visit or discontinued from study before or on the Day 29 study visit;
- Sponsor authorization of this SAP;
- Sponsor authorization of the analysis sets (refer to Section 5.3);
- Interim or final database lock of each sub-protocol contributing to the shared control group of the candidate agent, as applicable;
- Interim database lock of the concerned candidate agent database (refer to DM Interim Database Lock Plan).

The data cut-off date will be the date the last patient completed the Day 29 study visit or discontinued from the study before or on the Day 29 study visit, whichever occurs first.

With the following exception, all planned analyses identified in this SAP will be performed by CCI Biostatistics at the time of the primary analysis of a sub-protocol. The exception is the summary and analysis of the secondary efficacy endpoint incidence of sustained clinical recovery as confirmed by Day 60 (refer to Section 16.2.1.9) which will be performed at the time of the final analysis of a sub-protocol (refer to Section 4.4).

For each sub-protocol, additional outputs to be produced at the time of the primary analysis may be specified in sub-protocol SAPs.

CCI [Redacted]

The CCI Biostatistics study team will remain blinded to the results of the primary analysis. Once the programs have been produced and validated by the CCI Biostatistics study team in a blinded fashion, these programs will be sent to CCI Unblinded statistician, independent from the study team, who will apply the randomization schedule and provide to a pre-identified and limited number of people within the Sponsor of the concerned sub-protocol with a set of unblinded outputs. The list of the unblinded personnel (i.e., CCI Unblinded Biostatistics team members as well as recipients of the unblinded results sent by CCI Unblinded Biostatistician) will be documented in the Unblinding Plan, which will be finalized before the data cut-off for the first IDMC safety analysis.

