4.4. FINAL ANALYSIS

The final analysis for a candidate agent will take place after:

- Approximately 350 patients have been randomized to the active arm of the sub-protocol of interest and approximately 350 patients have been randomized to the shared placebo plus SoC control arm of the sub-protocol of interest (refer to Section 4.5), and last patient randomized into one of these two treatment arms is from the sub-protocol of interest, because if the last randomized patient is from a sub-protocol other than the one of interest, the patient’s treatment arm will automatically be unblinded since those patients can only be included in the shared placebo plus SoC control arm of the sub-protocol of interest;
- The last patient randomized to that candidate agent plus SoC treatment arm and its concurrent shared placebo plus SoC control arm (refer to Section 4.5) have had the opportunity to complete the Day 60 visit or discontinued from the study,
- Sponsor authorization of this SAP,
- Interim or final database lock of each sub-protocol contributing to the shared control group of the candidate agent, as applicable;
- Final database lock of the concerned candidate agent.

Unless otherwise specified, definitions and derivations for the final analysis will be based on those required for the primary analysis contained in this SAP (refer to Section 4.3). The outputs to be produced at the time of the final analysis of a sub-protocol are:

- Summary of patient disposition (refer to Section 9.1);

CCI [Redacted]

Master Statistical Analysis Plan

- Summary of protocol deviations (refer to Section 9.2)
- Summary of concomitant medications (refer to Section 13);
- Summary and analysis of the incidence of sustained clinical recovery as confirmed by Day 60 (other secondary efficacy endpoint; refer to Section 16.2.3.1);
- Summary of all-cause mortality through Day 60 (additional efficacy endpoint; refer to Section 16.4.3);
- All summaries planned for the AEs (refer to Section 17.1).

For each sub-protocol, additional outputs to be produced at the time of the final analysis may be specified in sub-protocol SAPs.

[figure not shown]

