16.4. ADDITIONAL EFFICACY

16.4.1. ADDITIONAL EFFICACY ENDPOINT

16.4.1.1. Incidence of All-Cause Mortality through Day 60

An additional efficacy endpoint is the incidence of all-cause mortality through Day 60, defined as the proportion of patients having died due to any cause before or on Day 60. Patients death before or at Day 60 will be based on data captured on the *Death Details* page of the eCRF.

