16.4.2. MISSING DATA IMPUTATION METHOD FOR ADDITIONAL EFFICACY ENDPOINT

Patients with an unknown alive/death status at Day 60 will be considered as alive at Day 60.

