16.4.3. ANALYSIS OF ADDITIONAL EFFICACY ENDPOINT

The number and percentage of patients alive and dead through Day 60 (refer to Section 16.4.1.1) along with the two-sided 95% CI for the percentage of patients dead through Day 60 will be provided by treatment arm. Primary reason of death will also be summarized by treatment arm. No statistical inference will be performed for this endpoint but treatment effect estimate (i.e., relative risk, odds ratio) and two-sided 95% CI will be provided.

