16.4.5. SUPPLEMENTARY ANALYSES FOR ADDITIONAL EFFICACY ENDPOINT

The time to all-cause death through Day 60, in days, will be derived as follows:

- Time to all-cause mortality through Day 60 (days) =
(Date of death / Date of censoring - Date of Study Day 1 [refer to Section 6.1]) + 1.

The date of death will be taken from data captured on the *Death Details* page of the eCRF.

For patients who were alive or patients with an unknown alive status at the time of the analysis due to missing data, time to all-cause mortality will be censored at the latest date on which the patient was known to be alive before or on Day 60. The last date the patient was known to be alive will be the latest date collected on any page of the eCRF.

For patients who discontinued from the study before Day 60, time to all-cause mortality will be censored at the date of study discontinuation, as captured on the *Disposition* page of the eCRF.

Number and percentage of patients with and without the event will be presented by randomized treatment arm. For patients who did not meet the event, the main reason for censoring (refer to Section 16.1.1) will be summarized similarly.

The incidence of all-cause mortality through Day 60 along with its two-sided 95% CI by treatment arm will then be estimated using Kaplan-Meier survival curves of the time to all-cause mortality through Day 60. Kaplan-Meier survival curves by treatment arm will also be provided.

The 25th percentile, 50th percentile (median), and 75th percentile of time to all-cause mortality (days) with the corresponding two-sided 95% CIs based on the Kaplan-Meier survival curves for each treatment arm will be presented. The estimate of the SEs will be computed using Greenwood's formula, the CI for the median will be calculated according to Brookmeyer and Crowley (1982) and the CIs for the survival function estimates at above mentioned time points will be derived from the Kaplan-Meier estimates using the log-log transformation.

Finally, a Cox proportional hazard model will be performed, including the baseline clinical severity of 2 on the 8-point ordinal scale for clinical severity (yes or no), remdesivir use at baseline (yes or no) stratification variables, both as captured on the IWRS, country (region), and treatment arm as factors. Ties will be handled using the exact method. The hazard ratio of the candidate agent plus SoC vs. placebo plus SoC and its associated two-sided 95% CI will be provided.

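### Master SAP 4.3 and 4.4 mistime Day 60 mortality: it is run at the Day 29 cut-off with open follow-up counted as survival, and its Kaplan-Meier and Cox analyses are not listed for the final analysis

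*SAP*

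**What the plan says.** Four parts of the Master SAP bear on this.

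- **Section 4.3, scope.** "With the following exception, all planned analyses identified in this SAP will be performed" at the primary analysis. One item is held back: "The exception is the summary and analysis of the secondary efficacy endpoint incidence of sustained clinical recovery as confirmed by Day 60". On timing: "The data cut-off date will be the date the last patient completed the Day 29 study visit", or discontinued by then.
- **Sections 16.4.1 to 16.4.3, the endpoint.** "An additional efficacy endpoint is the incidence of all-cause mortality through Day 60". Deaths come from the death page of the case report form. The missing-data rule is one sentence: "Patients with an unknown alive/death status at Day 60 will be considered as alive at Day 60". Section 16.4.3 reports counts, percentages, a confidence interval, a relative risk and an odds ratio, and rules out statistical inference.
- **Section 16.4.5, supplementary analyses.** Kaplan-Meier curves of time to death through Day 60, and then: "Finally, a Cox proportional hazard model will be performed". Patients not known to have died are censored at the last date known alive, or at study discontinuation.
- **Section 4.4, final-analysis outputs.** The mortality item reads "Summary of all-cause mortality through Day 60 (additional efficacy endpoint; refer to Section 16.4.3". Section 16.4.5 is not listed. Sub-protocol SAPs may add outputs.

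**The concern.** Sustained recovery is held back from the primary analysis, evidently because Day 60 data are incomplete when the last patient is at Day 29. The same reason applies to Day 60 mortality, yet it is not held back. Two things follow if the text is programmed as written.

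First, the primary-analysis report carries a Day 60 death proportion in which some patients are survivors only because their Day 60 has not yet come. Second, the Day 60 survival curves and hazard ratio are produced at the primary analysis and not again, so no Day 60 hazard ratio is planned on complete follow-up. A reader would then have two different Day 60 death proportions, and a hazard ratio that rests on less follow-up than the final one.

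**Working it through.** **Reading the sections together.**

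1. Section 16.4 is a planned analysis of the Master SAP and is not the item excepted in 4.3. It is therefore run at the primary analysis.
2. Listing Day 60 mortality in 4.4 does not defer it. That list also contains disposition, protocol deviations, concomitant medications and adverse events, all of which 4.3 also runs at the primary analysis.
3. The 4.4 item cites 16.4.3 alone, so 16.4.5 is not repeated unless a sub-protocol SAP adds it.
4. The COV-01-004 SAP does not add it. Section 3.3 declares no changes, Section 4 adds only safety outputs at the final analysis, and Section 16 refers efficacy to the Master SAP. The COV-01-005 SAP has no primary analysis and places a Day 60 Kaplan-Meier analysis, without Cox, at its final analysis. The COV-01-001 SAP also has no primary analysis, and its text on this section is redacted.

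**Size.** The plan gives no figure for Day 60 mortality, so there is none to reproduce.

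Inputs from the Master SAP: 350 patients per arm, 700 in total (7.1); 15% control mortality through Day 29 (7.1); cut-off at the last patient's Day 29 (4.3).

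Assumptions, not in the documents: uniform enrolment over A days; further mortality m between Day 29 and Day 60, spread evenly over those 31 days; deaths before the cut-off are all recorded.

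- Patients randomized in the last 60 − 29 = 31 days have not reached Day 60. Their share is f = 31/A.
- A patient randomized u days before the last one has (31 − u)/31 of the Day 29 to Day 60 interval unseen. Averaged over u from 0 to 31, this is one half.
- Understatement in percentage points = 100 × f × 0.5 × m. Deaths not yet seen = 700 × f × 0.5 × m.

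| A (days) | f | Short of Day 60, of 700* | m = 1%: points (deaths) | m = 4%: points (deaths) |
|---|---|---|---|---|
| 90 | 34.4% | 241 | 0.17 (1.2) | 0.69 (4.8) |
| 180 | 17.2% | 121 | 0.09 (0.6) | 0.34 (2.4) |
| 365 | 8.5% | 59 | 0.04 (0.3) | 0.17 (1.2) |

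*Less any who died before the cut-off.

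Very fast enrolment over 60 days with m = 4% would give 100 × 0.517 × 0.5 × 0.04 = 1.03 points.

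**Precision of the hazard ratio.** Take m = 3% and apply the 15% to both arms. Total deaths by Day 60 are 0.18 × 700 = 126. Unseen deaths are 700 × f × 0.5 × 0.03 = 3.6, 1.8 or 0.9 for A = 90, 180 or 365. That is 0.7% to 2.9% of the 126. With the standard error proportional to 1/√(deaths), it rises by a factor of 1/√(1 − 0.007) to 1/√(1 − 0.029), or about 0.4% to 1.5%.

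**The case against.** The strongest reply is that little depends on this, and most of that reply stands. The 16.4.3 summary is on the 4.4 list, so the proportion, relative risk and odds ratio are recalculated after every patient has had the chance to complete Day 60. The endpoint is additional, has no formal test and lies outside the hierarchy in 7.4. The key secondary mortality endpoint is at Day 29, which is due for every patient at the primary cut-off.

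Several stronger readings are tempting, and the documents do not support them:

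- **That every patient short of Day 60 is counted as alive.** Under 16.4.1.1, deaths recorded before the cut-off count as deaths.
- **That the Kaplan-Meier and Cox analyses are biased toward survival.** The alive rule governs the proportion. Section 16.4.5 censors at the last date known alive, so what is lost is precision.
- **That the relative risk or odds ratio is distorted.** The control arm is concurrent (4.5), so the understatement should be broadly similar in both arms. No distortion has been shown.
- **That a complete-data analysis is missing in every sub-protocol.** It is the Master SAP default, and COV-01-005 departs from it for Kaplan-Meier.

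It can also be argued that a patient whose Day 60 is not yet due does not have missing data, so 16.4.2 was not meant to apply. That may be the intention. However, the sentence refers to unknown status without limiting it to missing data, as 16.4.5 does, and it makes no provision for patients still in follow-up.

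**Conclusion.** The gap is real and minor. As written, the primary-analysis report would understate Day 60 mortality by about 0.04 to 0.7 percentage points, or 0.3 to 4.8 deaths in 700. This range rests wholly on the assumed 90 to 365 days of enrolment and 1% to 4% further mortality. The final Day 60 proportion is not affected.

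Under the Master SAP default, the 16.4.5 survival curves and hazard ratio are produced only on incomplete Day 29 to Day 60 follow-up, with a standard error perhaps 0.4% to 1.5% larger than on complete data. Among the three sub-protocols this is live only for COV-01-004, and the documents do not show whether that primary analysis was reached. Alpha, power and the primary conclusion are unaffected.

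**What to change.** In Master SAP 4.3, extend the exception to all of Section 16.4, so that Day 60 mortality (16.4.3 and 16.4.5) waits for the final analysis. In 4.4, cite both 16.4.3 and 16.4.5 in the mortality item. No patient is then counted as alive merely because Day 60 has not arrived, and the Kaplan-Meier and Cox results rest on the same follow-up as the reported proportion.

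The cost is two lines of SAP wording and no new data. The downside is that Day 60 mortality results appear about one month later, with the final analysis.

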4.4. FINAL ANALYSIS

The final analysis for a candidate agent will take place after:

- Approximately 350 patients have been randomized to the active arm of the sub-protocol of interest and approximately 350 patients have been randomized to the shared placebo plus SoC control arm of the sub-protocol of interest (refer to Section 4.5), and last patient randomized into one of these two treatment arms is from the sub-protocol of interest, because if the last randomized patient is from a sub-protocol other than the one of interest, the patient’s treatment arm will automatically be unblinded since those patients can only be included in the shared placebo plus SoC control arm of the sub-protocol of interest;
- The last patient randomized to that candidate agent plus SoC treatment arm and its concurrent shared placebo plus SoC control arm (refer to Section 4.5) have had the opportunity to complete the Day 60 visit or discontinued from the study,
- Sponsor authorization of this SAP,
- Interim or final database lock of each sub-protocol contributing to the shared control group of the candidate agent, as applicable;
- Final database lock of the concerned candidate agent.

Unless otherwise specified, definitions and derivations for the final analysis will be based on those required for the primary analysis contained in this SAP (refer to Section 4.3). The outputs to be produced at the time of the final analysis of a sub-protocol are:

- Summary of patient disposition (refer to Section 9.1);

CCI [Redacted]

Master Statistical Analysis Plan

- Summary of protocol deviations (refer to Section 9.2)
- Summary of concomitant medications (refer to Section 13);
- Summary and analysis of the incidence of sustained clinical recovery as confirmed by Day 60 (other secondary efficacy endpoint; refer to Section 16.2.3.1);
- Summary of all-cause mortality through Day 60 (additional efficacy endpoint; refer to Section 16.4.3);
- All summaries planned for the AEs (refer to Section 17.1).

For each sub-protocol, additional outputs to be produced at the time of the final analysis may be specified in sub-protocol SAPs.

[figure not shown]
The CCI Biostatistics study team will remain blinded to the results of the final analysis of each subprotocol with the exception of the final analysis of the last sub-protocol reaching this milestone. Once the programs have been produced and validated by the CCI Biostatistics study team in a blinded fashion, these programs will be sent to CCI Unblinded statistician, independent from the study team, who will apply the randomization schedule and provide to a pre-identified and limited number of people within the Sponsor of the concerned sub-protocol with a set of unblinded outputs. The list of the unblinded personnel (i.e., CCI Unblinded Biostatistics team members as well as recipients of the unblinded results sent by CCI Unblinded Biostatistician) will be documented in the Unblinding Plan, which will be finalized before the data cut-off for the first IDMC safety analysis.

4.5. SELECTION OF THE CONTROL ARM FOR AN ANALYSIS

The subset of the placebo plus SoC group, regardless of which sub-protocol the placebo patient belongs, enrolled concurrently to an active agent with matching inclusion/exclusion criteria will serve as the control arm for the analysis of a candidate agent. An exception to this definition is that if a sub-protocol X is not open at a site for screening, the concurrent placebo from other active sub-protocol(s) at that site will not be eligible for inclusion in the control arm for sub-protocol X. This is because patient’s eligibility for sub-protocol X cannot be determined without sub-protocol consent and obtaining consent for a sub-protocol is not possible until that sub-protocol is opened at a site for screening. It is to be noted that a patient randomized to the placebo arm of sub-protocol X taking the candidate agent of sub-protocol Y for another approved indication (based on data collected on the *Concomitant Medications* page of the eCRF) at the time of randomization will not be eligible for the control arm of the sub-protocol Y.

For each sub-protocol and each site, ‘concurrently’ is defined as the period starting on the date the site was opened

CCI [Redacted]	[Redacted]	Version Number:	Amendment 1, v1.0
PPD [Redacted]	[Redacted]	Version Date:	23Apr2021
CCI [Redacted]	[Redacted]	[Redacted]	[Redacted]
[Redacted]	[Redacted]	[Redacted]	[Redacted]
[Redacted]	[Redacted]	[Redacted]	[Redacted]

for screening for the sub-protocol and ending on the date of the last patient randomized into that sub-protocol for an interim, primary, and final analyses. For IDMC safety analyses, the date of the data cut-off will be used in lieu of the date of the last patient randomized into the sub-protocol.

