## 5.6 Concomitant Medications

No dedicated drug interaction studies have been conducted with lanadelumab.

The use of immunomodulators (eg, methotrexate, azathioprine, 6-mercaptopurine, TNF $\alpha$  inhibitor, JAK inhibitor, alpha-integrin inhibitor) are prohibited during participation in the study.

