#### **3.2.1 Inclusion Criteria**

An additional inclusion criterion that is specific to the sub-protocol is as follows:

- X1. Antibiotic prophylaxis: PLEASE NOTE that all patients must be willing to take antibiotic prophylaxis concomitantly, starting with the first dose of zilucoplan or placebo.

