#### **5.6 Concomitant Medications**

To mitigate the risk of *Neisseria* infection, concomitant administration of antibiotic prophylaxis decided by the Investigator is required for a maximum of 28 days starting with the first dose of zilucoplan or placebo (ie, during study drug treatment and an additional 14 days after cessation of zilucoplan or placebo). Consultation with a local microbiologist and/or infectious disease specialist is recommended to select the appropriate antibiotic prophylaxis. Guidelines about treatment and prevention of *N. meningitidis*-caused meningitis should also be considered.

If the patient is discharged prior to finishing antibiotic prophylaxis, it can be confirmed by telephone at Day 29 if prophylaxis is completed at home.

Additional antibiotics can be administered as per the Investigator's judgment.

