The Master Protocol outlines the overall design of the study, including the population, inclusion and exclusion criteria, randomization scheme, primary, secondary, and exploratory endpoints, study design, statistical methodology, and planned analyses that are common for all candidate agents to be tested. The Master Protocol is structured such that multiple candidate agents from different pharmaceutical companies can be evaluated simultaneously. The plan is to add candidate agents as they are identified and/or to remove therapies based on results of interim analyses (IAs; e.g., due to futility or if they are considered unsafe). The shared placebo control group for a candidate agent will include only patients randomized during the same period in which the candidate agent is opened for enrollment (refer to Section 4.5). Patients will be randomized equally to either the candidate agent plus SoC or placebo plus SoC in a double-blind fashion. Patients who are randomized to placebo plus SoC will be subsequently randomized equally to a matching placebo corresponding to an available candidate agent whose sub-protocol the patient qualified for (i.e., a 2-stage randomization). Each patient in the placebo plus SoC group will receive one type of placebo. Therefore, patients may be aware of which sub-protocol they were randomized to but not whether they will receive active agent or placebo investigational product. The comparator group of a candidate agent will include patients randomized to any matching placebo for a candidate agent available at the time of randomization for that agent (refer to Section 4.5).

Patients will be screened on Day -1 (the day before the first dose of study treatment [candidate agent plus SoC or

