16. EFFICACY ENDPOINTS

Unless otherwise indicated, all efficacy summaries and figures will be presented by treatment arm and visit, when appropriate, based on the FAS. Listings will be provided for all efficacy data.

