17.1. ADVERSE EVENTS

Each AE will be classified as either:

- Prior, defined as any AE that started or worsened in severity on or after the date of signed informed consent but before the first dose of study drug;
- Treatment-emergent, defined as any AE that started or worsened in severity on or after the first dose of study drug.

If time of the first dose of study drug and time of start of AEs are available, then the times will be taken into account for determining TEAEs. Refer to [Appendix 1](#) for handling of partial and completely missing dates for AEs. In the case where it is not possible to define an AE as treatment emergent or not, the AE will be classified by the worst case; i.e. treatment emergent.

AEs will be coded using the MedDRA dictionary, version 23.1 or later. Summaries by System Organ Class and PT will be sorted as follows: System Organ Classes will be sorted in alphabetical order and within each System Organ Class, PTs will be sorted by decreasing order to total frequency.

An overall summary of number and percentage of patients within each of the categories described in the sub-sections below will be provided by treatment arm. Should a patient experience multiple events within a category, the patient will be counted only once for that category. Additionally, the risk difference of the overall incidence rates of serious TEAEs and overall incidence rates of AESIs (when applicable for a sub-protocol) between treatment and control arms will be presented along with its 95% two-sided Wald CI.

[figure not shown]
All AEs (prior and TEAE) will be listed.

CCI

PPD

Version Number: Amendment 1, v1.0
Version Date: 23Apr2021

CCI

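### Antibiotics are mandated in both zilucoplan arms but not in the other placebo groups pooled as control, and the efficacy summaries and serious-TEAE risk difference use only the pooled control

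*SAP*

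**What the plan says.** **Who gets antibiotics.** In the zilucoplan sub-protocol (COV-01-005, 5.6), "antibiotic prophylaxis decided by the Investigator is required for a maximum of 28 days starting with the first dose of zilucoplan or placebo". The requirement covers active and placebo patients alike. It is also an entry condition (3.2.1): "all patients must be willing to take antibiotic prophylaxis concomitantly, starting with the first dose of zilucoplan or placebo". The lanadelumab (COV-01-001) and apremilast (COV-01-004) sub-protocols contain no such mandate.

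**Who is the control.** Placebo patients are "subsequently randomized equally to a matching placebo corresponding to an available candidate agent whose sub-protocol the patient qualified for" (Master SAP 3.1). Master SAP 4.5 then pools them: "The subset of the placebo plus SoC group, regardless of which sub-protocol the placebo patient belongs, enrolled concurrently to an active agent", provided that eligibility matches. For the zilucoplan final analysis, COV-01-005 SAP 4.5.2 replaces this rule. It admits every placebo patient at a qualifying site, whatever the timing and whether or not the patient met zilucoplan's own entry criteria.

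**What is shown.** Under Master SAP 16, "all efficacy summaries and figures will be presented by treatment arm and visit", and Appendix 2 has a single placebo column. COV-01-005 SAP 16 follows the Master SAP and drops all efficacy inference. Master SAP 17.1 sets "the risk difference of the overall incidence rates of serious TEAEs" between the treatment and control arms. By contrast, disposition, demographics, disease history and medical history (Master SAP 9 to 12) do split the control by sub-protocol.

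**The concern.** The mandated co-treatment follows the sub-protocol, not the active-or-placebo assignment. Within COV-01-005 the two arms are alike in this respect. Once other placebo groups are pooled in, the zilucoplan arm is wholly under the mandate and the control only in part. Eligibility matching would not cure this, because the entry criterion secures willingness to take antibiotics, not receipt, and the zilucoplan final analysis drops eligibility matching anyway. The Master SAP models adjust for baseline severity stratum, remdesivir and country or region (7.6), and nothing there captures the difference.

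If the mandate changes recovery, rehospitalization, death or serious events in either direction, that change appears in the zilucoplan-versus-control display as though it belonged to the agent. The reverse holds for apremilast: zilucoplan-placebo patients who enter its control bring mandated antibiotics that the apremilast arm lacks.

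**Working it through.** **Design figures.** With 490 events, HR 1.364 and one-sided 0.025, fixed-design power is 93.0%. Adding the futility looks at 123 and 270 events gives 88.3%, with null stopping probabilities of 49.7% and 34.6%, as the Master SAP states. This point does not touch those figures.

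**Ceiling on zilucoplan's own placebo.** Inputs: 108 patients randomized into COV-01-005 (its SAP, 16), and about 7:1 active to control under the Master SAP definition (its SAP, 4.5.2). The arm counts behind 7:1 are not given, so that ratio cannot be recomputed. Let P be own placebo and A = 108 − P active. Own-placebo patients belong to the Master SAP control, so P ≤ A/7. Then 8P ≤ 108 and P ≤ 13.5, so at most 13. As 7:1 is approximate: 6:1 gives 108/7 = 15.4, at most 15; 8:1 gives 108/9 = 12.

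**Share of the zilucoplan control under the mandate.** The SAP expects fewer than one third of about 700 patients in the final analysis, so a total N below about 233. With P = 13, A = 95 and the control is C = N − 95. The share is s = 13/C. For fixed N, s rises with P, so these are ceilings given 7:1.

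| Assumed N | Control C | s | 1 − s |
|---|---|---|---|
| 233 | 138 | 9.4% | 90.6% |
| 200 | 105 | 12.4% | 87.6% |
| 150 | 55 | 23.6% | 76.4% |
| 121 | 26 | 50.0% | 50.0% |

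The documents give no lower limit for N. The control is mostly without the mandate whenever N exceeds 121.

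**What enters the contrast.** Let d be the effect of the mandate on a risk, net of antibiotics given as usual care. With no drug effect, the pooled risk difference is d − s·d = (1 − s)·d. At N = 233, about 91% of d is displayed as if due to zilucoplan. Against own placebo, none is.

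On the hazard scale, let h be the effect of the mandate on recovery. The documents do not give it, and I assume 0.9 to 1.2. For a null zilucoplan the apparent HR is about h/(s·h + 1 − s):

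| h | s = 9.4% | s = 50% |
|---|---|---|
| 0.9 | 0.91 | 0.95 |
| 1.1 | 1.09 | 1.05 |
| 1.2 | 1.18 | 1.09 |

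No HR is planned for zilucoplan, so this only scales what the Kaplan-Meier curves could show. At h = 1 the distortion is zero.

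**Apremilast.** The planned control is about 350 (Master SAP 4.3). At most 13/350 = 3.7% is zilucoplan placebo (12 to 15 patients: 3.4% to 4.3%). For a null agent the apparent HR is 1/(s·h + 1 − s): 1/0.9963 = 1.004 at h = 0.9 and 1/1.0074 = 0.993 at h = 1.2.

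**The case against.** Much of the case against a larger claim stands.

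- A reader might infer that the shared control is antibiotic-free. It is not. Zilucoplan-placebo patients must receive prophylaxis, and others may receive antibiotics as usual care; the apremilast sub-protocol lists antibacterials among the medications to record.
- A reader might take equal second-stage allocation to mean that one third (three agents) or one half (two agents) of every control is under the mandate. That is the design expectation. The reported 7:1 and 108 patients do not fit it.
- A reader might infer that bacterial infection, the expected risk of C5 inhibition, would be hidden. COV-01-005 SAP 17.1.1 makes infections, serious infections and Neisseria infections AESIs and summarizes them for COV-01-005 patients only. Master SAP 17 adds own-placebo safety summaries, and COV-01-005 SAP 13 reports antibiotic use by arm and for own placebo.
- A reader might fear that an efficacy test credits antibiotics to zilucoplan. No such test remains; COV-01-005 SAP 16 allows only within-arm summaries and intervals.
- A reader might see a mirror problem in lanadelumab, where immunomodulators "are prohibited during participation in the study". That sub-protocol expects about 34 patients and has no inference (COV-01-001 SAP 16). Its SAP also follows sub-protocol version 2.0, while the text available is version 1.2.

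Pooling was also a deliberate choice, and an own-placebo group of about 13 is too small to lead. These arguments limit the size and the remedy. They do not supply the missing comparison: no efficacy summary and no serious-TEAE risk difference against own placebo is specified.

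**Conclusion.** The point holds as a should-fix. The treatment difference is built into the sub-protocols, and two sets of zilucoplan outputs, the efficacy summaries and the serious-TEAE risk difference, cannot separate agent from mandated co-treatment. The effect there is on descriptive comparisons only. Most of the pooled zilucoplan control is probably outside the mandate, but the exact share is not given. For apremilast, the only agent here with inference still planned, the likely distortion is small.

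This rests on three assumptions: the 7:1 estimate is roughly right (the lanadelumab SAP prints the same figure), all own-placebo patients fell within the Master SAP control, and the apremilast control reaches about 350. A smaller apremilast control would raise the 4%. The direction and size of any antibiotic effect are unknown.

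**What to change.** 1. **COV-01-005 SAP 16 and 17.** Beside the pooled control, and not in its place, add a zilucoplan-placebo column to the efficacy summaries and a serious-TEAE risk difference against zilucoplan placebo. Add a note that the other pooled controls had no mandated prophylaxis.
2. **Master SAP 16.1.5 and 16.2.5, for COV-01-004.** Add one supplementary analysis of the primary and key secondary endpoints that excludes COV-01-005 placebo patients from the control.

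Both use assignments already recorded, follow what the zilucoplan SAP already does for AESIs, and leave patient care unchanged. The cost of (1) is imprecision: with 13 patients and a proportion near 50%, the 95% half-width is about 1.96 × √(0.25/13) = 27 percentage points. The cost of (2) is slight: losing 13 of about 700 patients removes about 490 × 13/700 = 9 events. Programming is a little more work in both.
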